### 946 **5.3 Primary Analysis – Symptom Success at One Year**

947 For each of the modality/condition groups, the primary analysis will be an estimation of the  
948 proportion of patients of patients with treatment success based on improvement of symptoms at  
949 10 weeks post intervention and at one year, with 95% confidence intervals.  
950

951 Table 4 shows the criteria for symptom success for each condition, which will be used to assess  
952 all treatment modalities.  
953

954 **Table 4: One-Year Symptom Success Criteria for Each Condition**

Condition	One-Year Symptom Success Criteria
CI	improvement of CI Symptom Survey (CISS) score of at least 9 points AND a score of <21 points
DI	diplopia no more than rarely in the past week in the primary position (question #1.1 on the Diplopia questionnaire)
HT	diplopia no more than rarely in the past week both in the primary position and for reading (questions #1.1 and #1.2 on the Diplopia questionnaire)

955 For patients who initiate a new treatment before completing one year of follow-up, the symptom  
956 success/failure status from the visit at which treatment was changed (i.e., the 10-week interim  
957 visit or an early outcome visit) will be brought forward as their one-year outcome.  
958

960 Rubin's multiple imputation will be used to impute outcome for patients who have not changed  
961 treatments but who are lost to follow-up or withdraw from the study prior to one-year  
962 exam.

963

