1
2
3
4
5
6
7
8
9
10
11
12
13

**Study of Adult Strabismus (SAS1)
Treatment and Outcomes in Subjects Enrolled with Divergence Insufficiency**

**Statistical Analysis Plan
Version 1.0**

Statistical Analysis Plan Version: 1.0, 04Jun2020
Protocol Version: 2.0, 11Apr2016

VERSION HISTORY

The following table outlines changes for the analysis plan:

VERSION NUMBER	AUTHOR	APPROVER	EFFECTIVE DATE	REVISION DESCRIPTION
1.0	[name]	[name]	04Jun2020	The statistical analysis plan was started prior to the analysis of data but was completed after an initial draft of the manuscript was written.

14
15
16
17
18
19
20
21
22
23

Signature of author: _____

Signature of approver: _____

24 **1.0 Overview**

25

26 **1.1 Study Synopsis**

27 Adults diagnosed with divergence insufficiency (DI) were enrolled if eligibility criteria
28 were met and one of the following treatments (subsequently referred to as treatment
29 modalities) were prescribed at the enrollment visit: Botox, orthoptic exercises, prism, or
30 surgery. The prescription of treatment for strabismus was at investigator discretion and
31 was used to identify eligible participants. Treatment assignment was not part of the
32 protocol.

33

34 **1.2 Manuscript Objective**

35 This study was designed to accomplish two study objectives:

- 36 • To describe clinical characteristics, symptoms, and prescribed treatments of adults
37 diagnosed with DI at enrollment
- 38 • To characterize symptoms and clinical outcomes at 10 weeks and 12 months after
39 the initiation of treatment

40

41 **1.3 Primary Outcome: Treatment Success**

42 The primary outcome is the proportion of participants who met success criteria. Success
43 is evaluated at 10 weeks and at 12 months after treatment was initiated.

44

45 At each timepoint, participants were classified as successfully treated if **all** the following
46 criteria were met:

- 47 • Participant indicated on the diplopia questionnaire (DQ) that diplopia in the
48 distance was experienced “rarely” or “never” during the last week
- 49 • Additional treatment (defined in section 4.0) was NOT received prior to the office
50 visit

51

52 **2.0 Treatment at Enrollment**

53 Participants were eligible for the study if one of four treatments was initiated at the
54 enrollment visit:

- 55 1. Botox injection
- 56 2. Newly prescribed orthoptic exercises
- 57 3. Newly prescribed prism
- 58 4. Surgery

59

60 Newly Prescribed Prism

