100 month visit, the 12-month visit served as both the outcome visit for the initial treatment
101 and the enrollment visit for second treatment.

102

103 When data are analyzed, participants who were re-enrolled may contribute two outcomes
104 to the analysis, one reflecting the results of prism treatment or orthoptic exercises, which
105 was the initial prescribed treatment, and the other reflecting the results of strabismus
106 surgery or Botox injection, which was received after the participant was re-enrolled. Even
107 though some participants may contribute multiple outcomes to the analysis, there will be
108 no adjustment for the potential correlation between these outcomes. Botox and strabismus
109 surgery result in permanent changes to the ocular system and are not expected to be
110 influenced by prior treatment with orthoptic exercises or prism. Therefore, it is safe to
111 assume that outcomes collected for the initial treatment are independent of outcomes
112 collected after re-enrollment.

113

114 **4.0 Additional or Newly Initiated Treatment during Follow Up**

115 Investigators were encouraged to observe enrolled participants for 12 months before
116 initiating new treatment. However, given that this is an observational study, investigators
117 were not limited in their ability to change existing treatment or to initiate new treatment.
118 In a general sense, treatment prescribed after enrollment may be classified as “additional
119 treatment” (also referred to as “newly initiated treatment”), but this definition depends on
120 the treatment initiated at enrollment and the timing of the newly initiated treatment.
121 Below are definitions of additional treatment.

122 Prism group

123 Participants enrolled following the prescription of prism were considered to have
124 received additional treatment at 10 weeks if the treatment history form at 10 weeks
125 indicated that Botox, orthoptic exercises, or surgery was received prior to the office visit.
126 At 12 months, participants were considered to have received additional treatment if the
127 treatment prescribed form at 10 weeks or the treatment prescribed form at 12 months
128 indicated that Botox, orthoptic exercises, or surgery was prescribed or received.

129
130
131 When evaluating treatment success within prism subgroups (low-relieving prism, high-
132 relieving prism, correcting prism), the prism prescription at follow-up was taken into

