133 consideration as well. In addition to the definition provided above, participants were
134 considered to have received additional treatment if there was an increase in the prism
135 prescription after enrollment. Participants were considered to have received additional
136 treatment at 10 weeks if the treatment history form at 10 weeks indicated that the
137 magnitude of the prism prescription had increased since enrollment. Participants were
138 considered to have received additional treatment at 12 months if the treatment prescribed
139 form at 10 weeks or the treatment history form at 12 months indicated that the magnitude
140 of prism prescribed had increased since enrollment.

141 Surgery group

142 Participants who were prescribed surgery at enrollment were considered to have received
143 additional treatment if the treatment history form at 10 weeks indicated that Botox or
144 surgery was received prior to the office visit. Participants were considered to have
145 received additional treatment at 12 months if the treatment prescribed form at 10 weeks
146 or the treatment history form at 12 weeks indicated that Botox, orthoptic exercises, prism,
147 or surgery was prescribed or received.

148 **5.0 Primary Analysis**

149 The following were tabulated by treatment prescribed at enrollment:

- 150 • The number and proportion of participants who met success criteria at distance
151 (see Section 1.3) at 10 weeks
- 152 • The number and proportion of participants who met success criteria at distance
153 (see Section 1.3) at 12 months

154 A 95% Clopper-Pearson confidence interval was calculated for each proportion.

159 Participants were included in analysis only if the DQ was completed at the visit. There
160 was one exception to this rule, participants were considered a failure if additional
161 treatment was received prior to the visit. If the 10-week treatment history form indicated
162 that additional treatment was received prior to the 10-week visit, the participants was
163 considered a failure both at 10 weeks and at 12 months. If the 12-month treatment history
164 form or the 10-week treatment prescribed form indicated that additional treatment was
165 received prior to the 12-month visit, then the participant was considered a failure at 12
166 months. When additional treatment was received prior to the visit, the participant was
167 counted in the denominator but not the numerator when calculating the success

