168 proportion. It is acknowledged that this procedure is biased unless the 10-week and 12-
169 month DQ data are not missing at random (NMAR), with those who missed that visit
170 being in truth more likely to be failures than those who completed the visit. In that case,
171 this procedure may be less biased. If the data are missing completely at random (MCAR),
172 the resulting estimate of success is an underestimate.

173

174 **6.0 Secondary Analyses**

175 Data collected after additional treatment was received was no longer representative of the
176 treatment initiated at enrollment. Consequently, data were excluded from analyses and
177 tabulations if additional treatment was prescribed or received prior to the visit, unless
178 otherwise specified.

179

180 **6.1 Number and Proportion of Participants that Received Each Treatment**

181 The number and proportion of participants that were prescribed each treatment at
182 enrollment was tabulated. Participants who were re-enrolled will be counted twice: once
183 for the initial treatment (orthoptic exercises or prism) prescribed at enrollment and again
184 for the second treatment (Botox or surgery), prescribed at re-enrollment.

185

186 **6.2 Participant characteristics at Enrollment and Medical History**

187 The following characteristics reported at enrollment were tabulated according to the
188 treatment initiated at enrollment:

189

- 190 • Sex
- 191 • Race/Ethnicity (White versus non-White)
- 192 • Age (18-24, 25-34, 35-44, ..., 75-84, 85-91)
- 193 • Whether or not refractive correction (spectacles or contact lenses) was
194 worn at the office visit
- 195 • Prior treatment for strabismus (orthoptic exercises, prism, none)
- 196 • Coexisting neurological conditions (Parkinson's, progressive supranuclear
197 palsy, basal ganglia disease, stroke, intracranial tumor)
- 198 • Other conditions (epiretinal membrane; age-related macular degeneration;
199 macular pathology; heart disease; diabetes; autoimmune disease;
200 significant head trauma; hypertension; cancer of bladder, breast, or
201 prostate)

201

202 The mean, standard deviation, median, and interquartile range (IQR) will be calculated
203 for age at enrollment.

204

205 **6.3 Clinical Characteristics at Enrollment**

206 The following clinical characteristics measured at enrollment were tabulated according to
207 the treatment initiated at enrollment:

- 208 • Frequency of diplopia at distance during the last week

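### For the primary divergence-insufficiency outcome, SAP 1.3 and 5.0 replace both Protocol 5.3 rules, for treatment changers and for missing outcomes, without saying so or giving a reason

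*SAP*

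**What the plan says.** Protocol 5.3 has two rules for the one-year outcome. For a patient who starts a new treatment, it takes the "success/failure status from the visit at which treatment was changed (i.e., the 10-week interim" visit or an early outcome visit) and uses it as the one-year result. For a patient who has not changed treatment but is lost or withdraws before the one-year exam, it uses multiple imputation. Protocol 5.5.2 asks for similar handling at 10 weeks. Protocol 3.5 requires an early outcome exam whenever a new treatment starts, so the study was set up to collect what carry-forward needs.

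The SAP names Protocol 2.0 as its basis. SAP 1.3 adds a condition to the definition of success: "Additional treatment (defined in section 4.0) was NOT received prior to the office" visit. SAP 5.0 then states: "Participants were included in analysis only if the DQ was completed at the visit". The one exception is that participants with additional treatment stay in the denominator as failures. Imputation and carry-forward appear nowhere in the SAP.

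SAP 5.0 does disclose possible bias. It says that if data are missing completely at random (MCAR), "the resulting estimate of success is an underestimate", and that the procedure may be less biased if those who missed the visit were more often failures.

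**The concern.** Success per treatment group is the primary result, and the analysis that the protocol specified for it is never shown. The two departures differ in kind. Counting every changer as a failure changes the quantity estimated: it becomes success without additional treatment, whatever the symptoms were at the change. Dropping non-changers without a diplopia questionnaire (DQ) keeps that quantity but can bias its estimate.

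The reader cannot undo either step. The number dropped can be worked out, because SAP 6.1 tabulates "The number and proportion of participants that were prescribed each treatment at" enrollment and 5.0 gives the denominator. The number of changers and their symptom status at the change are not planned to be reported, so the dependence on the changer rule stays hidden.

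**Working it through.** **1. The plan's own precision.** Protocol 5.2: 50 per group, up to 5% loss. 50 x 0.95 = 47.5, taken as 47. Half-width at 50% success = 1.96 x sqrt(0.25/47) = 14.3 points, which agrees with the stated 14. The SAP's Clopper-Pearson interval at 23/47 runs from 34.1% to 63.9%, a half-width of 14.9 points. This is the yardstick for what follows.

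**2. The rules side by side (12 months).**

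| Participant | Protocol 5.3 | SAP 1.3 and 5.0 |
|---|---|---|
| Changer, failure at change | failure | failure |
| Changer, success at change | success | failure |
| Non-changer, lost or withdrawn | imputed | dropped |
| Non-changer with DQ | observed | observed |

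**3. Who falls in the second row.** Protocol 3.5 and SAP 3.0 allow re-enrollment into surgery or Botox only if eligibility is met again. Protocol 2.2.2 requires distance diplopia sometimes or worse; success requires rarely or never. A properly re-enrolled changer was therefore a failure at the change, and the two rules agree. Only changers who were not re-enrolled can differ, for example those with prism added after surgery.

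The rule mainly affects 12 months. At 10 weeks only treatment received before that visit counts, and for the surgery group SAP 4.0 then counts only Botox or surgery. A change made at the 10-week visit leaves the 10-week status untouched.

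Reduction in success = b x s, where b = share of the group who changed and were not re-enrolled, and s = proportion of those who were successes at change. The documents give neither, so these values are assumptions:

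| b | s = 0 | s = 20% | s = 50% |
|---|---|---|---|
| 10% | 0 | 2 points | 5 points |
| 20% | 0 | 4 points | 10 points |

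In a group of 50, one such participant is worth 1/50 = 2 points.

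**4. Missing-data rule under MCAR.** Let a = share of all changers, p = success among non-changers, m = share of non-changers without a DQ.

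Bias = (1-a)(1-m)p / [a + (1-a)(1-m)] - (1-a)p

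Assumed: a = 10-40%, p = 60-80%.

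- m = 5%, a = 10%, p = 60%: 0.513/0.955 - 0.540 = -0.3 points.
- m = 5%, a = 40%, p = 80%: 0.456/0.970 - 0.480 = -1.0 points.
- m = 20%, same two corners: 0.432/0.820 - 0.540 = -1.3 and 0.384/0.880 - 0.480 = -4.4 points.

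This takes every changer as identified. If changers who miss the visit are dropped too, the MCAR bias moves towards zero.

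**5. Missingness that depends on outcome.** In general, bias = w(E - q), where w = share of the group dropped, E = reported proportion and q = true composite success of those dropped. Check at a = 20%, m = 5%, p = 70%: w = 0.80 x 0.05 = 4%, E = 0.532/0.960 = 55.4%, and 0.04 x (0.554 - 0.70) = -0.58 points, the same as the formula in step 4. If all those dropped were failures, the bias is +0.04 x 0.554 = +2.2 points; if all were successes, -0.04 x 0.446 = -1.8 points. For E between 40% and 80%, the limits -w(1-E) and +wE span -3.0 to +4.0 points at w = 5%, and -12 to +16 at w = 20%.

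**6. Both rules together.** Assume 50 enrolled, 5 changers, 3 lost non-changers, 70% success among non-changers, and imputation at that rate. SAP: 0.70 x 42/47 = 62.6%. Protocol: (0.70 x 45 + 5s)/50, where s is now averaged over all changers. This gives 63.0% at s = 0 and 66.0% at s = 30%. The 0.4-point gap at s = 0 comes from the missing-data rule; the rest comes from the changer rule.

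**The case against.** The SAP's composite is a legitimate outcome, and for a descriptive study arguably the more informative one. SAP 5.0 is open about possible bias. SAP 6.0 says that data after additional treatment no longer represent the initial treatment. At the planned loss the missing-data effect is trivial against the interval width, and re-enrolled changers are classified alike by both rules.

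Most of this stands, and it limits the size of the point. It does not supply the missing reason. The bias note never mentions Protocol 5.3. The remark in 6.0 is written for the secondary analyses, and it does not argue against carry-forward, which uses status at the change, before the new treatment can act.

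Two stronger readings are tempting. A reader might infer that the changer rule could lower success by as much as 20 points (40% changers x 50% successes at change). That applies one success share to all changers, although those re-enrolled contribute zero. A reader might also infer that the SAP's MCAR sentence is wrong. For the procedure it describes, with changers kept in the denominator and non-completers dropped, it is correct. What it omits is that the estimate can be too high. That needs those dropped to have done worse than the reported proportion E, and not merely worse than the non-changers who completed the visit.

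**Conclusion.** The departure is in the text and should be corrected: both Protocol 5.3 rules are replaced for the primary DI outcome, with no acknowledgement, no reason and no protocol-rule analysis.

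Its size is modest or unknown. The missing-data rule shifts the estimate by about -0.3 to -1.0 points at the planned loss of up to 5%, under MCAR and the assumed 10-40% changers and 60-80% success. It matters only if loss is clearly higher or depends on outcome. The 5% is a planning figure, not an observed one. The changer rule has no effect on re-enrolled participants. For the rest it equals b x s, which the documents do not allow anyone to compute.

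The SAP's version history says that it was started before the analysis and completed after an initial manuscript draft. A reader might infer that the rules were chosen from results. The documents do not show that, nor when the rules were set. The timing is a reason to state the justification, and no more than that.

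**What to change.** 1. Add to SAP 5.0, at 12 months and similarly at 10 weeks, an analysis under the Protocol 5.3 rules: status at change carried forward from the 10-week or early outcome exam, and multiple imputation for non-changers who are lost or withdraw. Protocol 5.3 is silent on changers with no exam at the change, attenders without a DQ, the imputation model and the interval method. Label choices on these as added assumptions, not as protocol-specified.
2. Keep the SAP composite with its Clopper-Pearson intervals, labelled *success without additional treatment*. State which result is primary, and give the reason for departing from Protocol 5.3.
3. Report by group and visit the number with additional treatment, how many were re-enrolled, their symptom status at change, and the number with missing DQs.
4. Add to the bias statement in 5.0 that the estimate is too high if those dropped would have succeeded less often than the reported proportion.

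Separate minor corrections:

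- For the prism group at 12 months, SAP 4.0 names the "treatment prescribed form at 10 weeks or the treatment prescribed form at 12 months", while 5.0 uses the 12-month history form.
- The exception in 6.4 is narrower than in 5.0 (10-week forms only, failure only at 12 months).
- 6.4 cites Section 4.0 for a bias note that stands in 5.0.

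The cost is SAP wording, one re-run, and a check of whether an exam exists for each changer. The downsides are two labelled results and reliance on missing at random for the imputed one; imputation removes little of a bias that depends on the unseen outcome itself.

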61 Participants who received newly prescribed prism were further categorized into the
62 following subgroups, based on the amount (percent) of the underlying deviation that was
63 corrected by the prism prescribed at enrollment:

- 64 • Low relieving prism (0 to <60% of underlying deviation corrected)
- 65 • High relieving prism (60 to <100% of underlying deviation corrected)
- 66 • Correcting prism (\geq 100% of underlying deviation corrected)

67

68 The percent of the deviation corrected by prism at enrollment is defined as

69 $\frac{\text{total prism prescribed at enrollment}}{\text{magnitude of distance deviation}} \times 100$, where

- 70 • Total prism prescribed at enrollment is defined as the sum of the prism
- 71 prescriptions in the left and right eyes at enrollment
- 72 • Magnitude of distance deviation is the size of the distance deviation measured by
- 73 prism and alternate cover test (PACT)

74

75 Surgery

76 Participants who received surgery were further categorized into the following groups
77 based on the type of surgery performed:

- 78 • Bilateral medial rectus recession
- 79 • Bilateral lateral rectus resection
- 80 • Other including:
 - 81 ○ Bilateral medial rectus muscle recession, superior rectus muscle nasal pole
 - 82 recession
 - 83 ○ Bilateral medial rectus muscle recession, superior rectus muscle recession
 - 84 ○ Bilateral lateral rectus muscle resection with superior transposition
 - 85 ○ Bilateral medial rectus muscle recession with superior transposition
 - 86 ○ Lateral rectus muscle tuck/plication, superior rectus muscle recession
 - 87 ○ Medial rectus muscle recession, lateral rectus muscle resection
 - 88 ○ Single medial rectus muscle recession
 - 89 ○ Single lateral rectus muscle tuck/plication

90

91 **3.0 Re-enrollment**

92 Participants enrolled into the prism and orthoptic exercises groups were given the option
93 to re-enroll into the study if Botox or strabismus surgery was prescribed at the 10-week
94 or 12-month office visit, and all other eligible criteria were met.

95

96 For participants who were re-enrolled following the prescription of strabismus surgery at
97 the 10-week visit, the 10-week visit served as both the outcome visit for the initial
98 treatment (prism or orthoptic exercises) and the enrollment visit for the second treatment
99 (Botox or strabismus surgery). Similarly, for participants who were re-enrolled at the 12-

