- 209 • Frequency of diplopia in reading position during the last week
- 210 • Horizontal deviation at distance (measured using PACT)
- 211 • Horizontal deviation at near (measured using PACT)
- 212 • Whether or not prism was needed to fuse in free space at distance

213

214 The mean, standard deviation, median, and IQR were tabulated for the following:

- 215 • Horizontal deviation at distance (measured using PACT)
- 216 • Horizontal deviation at near (measured using PACT)
- 217 • DQ score
- 218 • Adult-Strabismus (AS-20) general function score
- 219 • AS-20 reading function score
- 220 • AS-20 self-perception score
- 221 • AS-20 interaction score

222

223 **6.4 Secondary Definition of Success: Successful Treatment at Both Distance and**
224 **Near**

225 Successful treatment at both distance and near is defined as diplopia reported “rarely” or
226 “never” both in the reading position and in the distance, and no additional treatment
227 prescribed.

228

229 The following were tabulated by treatment prescribed at enrollment:

- 230 • The number and proportion of participants who met success criteria at both
231 distance and near at 10 weeks
- 232 • The number and proportion of participants who met success criteria at both
233 distance and near at 12 months

234

235 A 95% Clopper-Pearson confidence interval was calculated for each proportion.

236

237 Participants were included in analysis only if the DQ was completed at the visit. There
238 was one exception to this rule. If the treatment history form or the treatment prescribed
239 form at the 10-week visit indicated that additional treatment was received, then the
240 participant will be considered a failure at 12 months. It is acknowledged this procedure
241 may be biased (see Section 4.0).

242

243 **6.5 Successful Treatment within Prism and Surgery Subgroups**

244 The following were tabulated within prism and surgery treatment subgroups:

- 245 • The number and proportion of participants that met success criteria at distance at
246 10 weeks
- 247 • The number and proportion of participants that met success criteria at both
248 distance and near at 10 weeks

- 249 • The number and proportion of participants that met success criteria at distance at
250 12 months
251 • The number and proportion of participants that met success criteria at both
252 distance and near at 12 months
253

254 A 95% Clopper-Pearson confidence interval was calculated for each proportion.
255

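### The SAP's sources for flagging additional treatment at 12 months contradict each other and omit the protocol's early outcome exam, so failure in the primary outcome is not uniquely defined

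*SAP*

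**What the plan says.** **Primary outcome.** SAP 1.3 requires diplopia at distance no more than rarely, and no additional treatment received before the visit. It refers to 4.0 for what counts as additional treatment.

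**Who is analysed.** Under SAP 5.0 a participant needs a completed diplopia questionnaire (DQ) at the visit. There "was one exception to this rule, participants were considered a failure if additional" treatment came before the visit, and that person is "counted in the denominator but not the numerator when calculating the success" proportion. Sections 6.5 and 6.7 repeat the general rule.

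**Which records show additional treatment at 12 months.**
- 5.0: the 10-week history form (failure at both time points), or the 12-month history "form or the 10-week treatment prescribed form indicated that additional treatment was" received before the 12-month visit.
- 4.0, prism group: the "treatment prescribed form at 10 weeks or the treatment prescribed form at 12 months", for treatment prescribed or received.
- 4.0, prism subgroups, for an increase in prism: the 10-week prescribed form or the 12-month history form.
- 4.0, surgery group: the 10-week prescribed form "or the treatment history form at 12 weeks indicated that Botox, orthoptic exercises, prism" or surgery.
- 6.4: the exception applies if the history or prescribed "form at the 10-week visit indicated that additional treatment was received, then the" participant fails at 12 months.
- 4.0 has no paragraph for exercise or Botox starters, although SAP 2.0 lists both as enrolled treatments.

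**Treatment changes between visits.** SAP 3.0 offers prism and exercise starters the option "to re-enroll into the study if Botox or strabismus surgery was prescribed at the 10-week" or 12-month visit. Protocol 3.5 instead requires an early outcome exam whenever a new treatment is initiated. Participation then ends for prism or exercise starters who begin the other of the two, for new surgery or Botox in a category that has closed, and for re-operation or re-injection. Under protocol 5.3 the symptom status from the 10-week "visit or an early outcome visit) will be brought forward as their one-year outcome". The SAP does not mention the early exam.

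**The concern.** Whether a participant received additional treatment decides whether he or she is a failure, is judged by the DQ, or is left out. With few participants per group, one reclassification is visible in the reported proportion. If the sections point to different records, two analysts following the SAP can produce different primary results from the same data.

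The early exam matters most. Someone who changes treatment after week 10 and leaves need not appear on any 10-week form and has no later 12-month visit. If the early exam is not a source, that person has no 12-month DQ and no flag, and can fall out of the denominator. The bias note in SAP 5.0 discusses missed visits and says that success is underestimated if data are missing completely at random. It does not mention an upward effect from unflagged exits.

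**Working it through.** **1. The 12-month source lists side by side**

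| Section | 10-wk history | 10-wk prescribed | 12-mo history | 12-mo prescribed | Early exam |
|---|---|---|---|---|---|
| 4.0 prism | no | yes | no | yes | no |
| 4.0 prism subgroups (prism increase) | no | yes | yes | no | no |
| 4.0 surgery | no | yes | given as 12 weeks | no | no |
| 4.0 exercises, Botox | none | none | none | none | none |
| 5.0 | yes | yes | yes | no | no |
| 6.4 exception | yes | yes | no | no | no |
| Protocol 5.3 | status at the 10-week visit, if treatment changed then | | | | yes |

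Protocol 3.2 schedules follow-up visits at 10 weeks and 12 months only.

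**2. How the rules classify the same person**

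- *Prism starter, DQ success at the scheduled 12-month visit, surgery first prescribed there.* Under 1.3 and 5.0 nothing was received before the visit, so this is a success. Under 4.0 the 12-month prescribed form makes it a failure.
- *Prism starter whose new treatment appears only on the 12-month history form.* A failure under 5.0. Not flagged under the 4.0 prism list.
- *Surgery starter with a re-operation planned between the two visits.* There is an early exam, then exit. The general sentence in 5.0 intends a failure. If the exam has its own form, none of the named forms shows the change and there is no 12-month DQ, so the person drops out. If the exam was filed on 12-month forms, the re-operation is prescribed but not yet received, and the DQ status can count, as in protocol 5.3.
- *Exercise starter who begins prism between visits.* 4.0 does not say what counts.

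Changes prescribed at week 10 are caught by the 10-week prescribed form. Surgery or Botox starters who add prism or exercises stay to 12 months under protocol 3.5. Neither group is lost.

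**3. The plan's own denominator (protocol 5.2)**

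50 × 0.95 = 47.5, stated as about 47. Half-width: 1.96 × √(0.25/47) = 14.3%, stated as 14%. Both reproduce and are not in dispute. They serve as a yardstick.

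**4. Size**

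One person reclassified between success and failure in a group of 50 moves the proportion by 1/50 = 2.0 points.

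For exits dropped from the denominator, let n be the group size, r the exits, p the success proportion in the rest, and s the success proportion at the early exam:

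p − [p(n − r) + s·r]/n = r(p − s)/n

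Setting s = 0 compares with the SAP's failure rule. Other values of s compare with protocol 5.3. The documents give neither r, p nor s, so all are assumed. Effect per exit (r = 1, n = 50), in points:

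| Comparison | p = 60% | p = 70% | p = 80% |
|---|---|---|---|
| SAP failure rule (s = 0) | +1.2 | +1.4 | +1.6 |
| Carry-forward, s = 25% | +0.7 | +0.9 | +1.1 |
| Carry-forward, s = 50% | +0.2 | +0.4 | +0.6 |
| Carry-forward, s = 75% | −0.3 | −0.1 | +0.1 |

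In a group of 20, the first row becomes 3.0, 3.5 and 4.0.

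Illustration, all inputs assumed: 50 participants, 4 exits of whom 1 was a success at the early exam, and 32 successes among the other 46, with the SAP's Clopper-Pearson intervals:
- exits dropped: 32/46 = 69.6% (54.2 to 82.3%)
- exits counted as failures: 32/50 = 64.0% (49.2 to 77.1%)
- early-exam status carried forward: 33/50 = 66.0% (51.2 to 78.8%)

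Dropping gives 5.6 points more than the failure rule and 3.6 more than carry-forward. If the exams were filed on 12-month forms in a prism group, the 4.0 list gives 64.0% because the new prescription is on the prescribed form. The 5.0 list can give 66.0%, because nothing had yet been received.

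**The case against.** The strongest reply is that SAP 5.0 already covers these people. Its exception is first stated without reference to any form and closes with a general denominator rule, so the form sentences between can be read as implementation. That stands as to intent. But those sentences are what a programmer would follow, they reach scheduled-visit forms only, and 6.4 lacks the general sentence.

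Second, protocol 3.5 has the early exam follow the follow-up procedures in 3.3, which collect treatments received and the DQ, so filing on 12-month forms is plausible. This also stands as a possibility. Neither document states it, and it would not settle prism, where 4.0 and 5.0 would still disagree.

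Third, there may have been no such exits. SAP 4.0 says investigators were encouraged to wait 12 months before starting new treatment, and SAP 3.0 describes re-enrollment at scheduled visits only. With no exits the omission of the early exam costs nothing. The conflict over treatment first prescribed at the 12-month visit would remain.

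The 12-week reference is evidently a slip, since its sentence concerns 12 months. It needs correction but carries little weight.

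A reader might infer that the reported 12-month success is inflated, or that the SAP excludes treatment changers by design. The documents support neither. The general rule says the opposite of exclusion, the number of exits and the filing practice are unknown, and against protocol 5.3 the sign can go either way.

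**Conclusion.** The concern holds as a defect of definition in the primary outcome. The 12-month source lists in SAP 4.0, 5.0 and 6.4 differ, two of the four enrolled treatments have no definition, and the exam on which the protocol relies for treatment changers is not named. On the text, the 4.0 prism rule and the rule in 1.3 and 5.0 classify the same participant differently.

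The numerical effect is unknown. If exits at the early exam were dropped, success is overstated against the SAP's own failure rule by 1.2 to 1.6 points per exit in a group of 50, assuming 60 to 80% success in the rest. Against protocol 5.3 the difference is positive when early-exam success is below that of the rest and negative when it is above. A single exit is small beside the planned half-width of 14 points; several would not be negligible. A biased result is not demonstrated. What is shown is that a reader cannot tell from the SAP whether these participants were dropped, counted as failures, or counted by their early-exam status.

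**What to change.** - Use one 12-month source list in SAP 4.0, 5.0 and 6.4: 10-week history, 10-week prescribed, 12-month history and early outcome exam forms. Sections 6.5 and 6.7 then follow.
- Remove treatment first prescribed at the scheduled 12-month visit from the 12-month failure rule, so that 4.0 agrees with 1.3 and 5.0. If early exams were filed on 12-month forms, say so and identify them, so that a prescription at an early exam is not confused with one at the scheduled visit.
- Correct the reference to 12 weeks in the surgery paragraph.
- Define additional treatment for exercise and Botox starters.
- Report the number of early-exam exits per treatment group.
- Report protocol 5.3's carry-forward of early-exam status as a sensitivity analysis beside the SAP's failure rule.

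The cost is SAP wording and some re-tabulation of data already collected. Success proportions may shift slightly in either direction, and the sensitivity analysis assumes that the last status before the change represents the one-year outcome.
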